## **QA AND QC PLAN**

### **11. Procedures in place to ensure the integrity and validity of the data**

The investigators and senior staff have all completed the required Human Subjects and HIPAA training in protecting people and their privacy during a research study and are under the supervision of Chestnut's IRB. Because there is the risk that some participants might be in jail or prison at some time during the follow-up period, the IRB has a prisoner representative, and we will secure approval from the NIH Office for Human Research Protections (OHRP) as well as secure a certificate of confidentiality from NIDA. All key research staff at CHS are or will be trained on the principles and process of informed consent through the Protecting Human Research Participants (PHRP) human subjects research online training program (<https://phrptraining.com>) and good clinical practice for clinical trials (<https://gcp.nidatrainig.org>) and then tested by their supervisors. All informed consents will be audiotaped for random review. If problems arise from the review, the PI and Protocol Monitor will meet with staff to correct the problem and meet with the participant when needed to clarify any potential confusion.

All PCs and web applications include password protection. Both use technical safeguards mandated by Health Information Technology for Economic and Clinical Health Act (HITECH) of 2009 for the transmission and maintenance of protected health information (PHI) and personal health records (PHR). As noted above, this includes using two-way encryption, check sum, double-keying, message authentication, digital signature,

Secure Sockets Layer (SSL), and password-protected accounts that define levels of access. The possibility of risk regarding confidentiality will be minimized by stripping all participant identifying information such as name, driver's license number, and social security number from all interview notes and electronic data files. Electronic study information will be kept on a file server that is secure, encrypted, and protected by password. Only authorized people will be allowed to see this information. Any study information that is kept on paper will be kept in a locked cabinet in a secure place. At the end of all study activities, the Chestnut Health Systems' research team will destroy all information that can identify participants.

## **12. Procedures to guarantee the accuracy and completeness of the dataset**

Drs. [name] and [name] will train and supervise research staff. Interviews are checked for completeness and relative to urine tests at office visits. All interviews will be digitally recorded and a random sample reviewed for quality assurance. Our QA process has previously produced consistently good psychometrics across staff, sites, and mode (in person vs. by phone). The GAIN electronic interview conducts range checks, makes simple and complex skips, and allows immediate consistency checks. If an interview needs to be done with paper and pencil (e.g., jail, hospital), the interviewer will field edit it followed by a second edit to verify that key fields are complete, provide feedback and/or get clarification of questions, and mark any missing/bad data. The Research Manager will review inconsistent or missing data with the interviewers. When the data are keyed, the computer system will again check for range and consistency across multiple items. Weekly management reports will be used to monitor performance and error reports will be reviewed weekly until there are no major problems (or when there is new staff), then monthly thereafter. All GAIN data will be checked for unexpected patterns of increased or decreased activity.

## **REGULATORY**

### **13. Reporting process for AEs and SAEs**

All expected and unexpected AEs and SAEs are reviewed by the PI and reported to the study's DSM monitor, Chestnut's IRB, and NIDA within 48 hours.

### **14. SAE reporting in medication trials: FDA, IRB, and NIDA**

Not applicable.

### **15. SAE reporting in non-medication trials: IRB and NIDA**

Any unexpected SAEs and or SAE related to the research are documented by staff, reviewed by the PI and reported to the study's DSM monitor, Chestnut's IRB, and NIDA within 48 hours.

### **16. Process of reporting IRB actions to NIDA**

Chestnut's IRB reviews any unexpected SAE or DSM concerns as they come up and every all AE/SAE for the project annually. They give their recommendations in writing that is reported to the NIDA as part of the annual continuation and can contact NIDA directly if they have concerns.

### **17. Process of changes or amendments to the protocol**

Any major changes or amendments to the study protocol (e.g., change in design, hypotheses, sample size, inclusion criteria) will typically be discussed in advance with the study's DSM monitor, Chestnut's IRB, and NIDA. The exception would be emergency steps taken to protect the safety or privacy of the study participants. In that event, we will notify the study's DSM monitor, Chestnut's IRB, and NIDA. Other minor changes (e.g., updates to software, adjusting instructions in surveys, updating applications) will be reported as part of the annual updates.

## **TRIAL SAFETY**

### **18. Potential risks and benefits for participants**

Though relatively low, there are potential risks associated with this study that we acknowledge to the participants during our consent process, intake assessment, and follow-up interviews, including:

- unauthorized disclosure of sensitive information collected by research staff during interviews
- discomfort may arise from issues that are addressed in the interview (e.g., family relationships, school, self-esteem, continued use)
- required disclosures if participants report a recent situation involving child abuse or neglect, or threat of harm to themselves or others

Participants may benefit directly by receiving help to access MAT for opioid use disorders, to stay in treatment, and to sustain recovery. Participants will be interviewed at baseline prior to randomization and at 3, 6, and 9 months post-randomization; they will be compensated at a rate of \$25 per assessment (interview and urine) for a possible total of \$100.

Participation may also benefit other people in the future by helping the field learn more about optimal mechanisms for linking individuals to MAT following an opioid overdose and factors that promote their sustained treatment retention and improvements in quality of life and overall psychosocial functioning and reduce poor health outcomes and risk of death.

#### **19. Risk mitigation plan (management of SAE and other study risks)**

As noted in section 11, we require all staff to get certified on human subject training and use HIPAA/HITECH compliant secure web services to house all of the data and limit access to be also encrypted means and role/password based by person. Expected negative events have are being documented both through the surveys/records (for expected events) and negative event forms (for unexpected events) - discussed further below. All consent/locator forms are kept in separate record systems/ locked files than the survey data. No confidential fields (e.g., names) are downloaded and data are further de-identified by replacing the dates with days from randomization, double-checking all text fields for any potential identifiers, and field research id with a second analytic research ID. The latter means that two linkage files are required to re-identify a person – one held by the analytic team in Bloomington-Normal and a second held separately by the field team in Chicago. No person will be identified in any study report. As discussed further below, expected and unexpected problems that have occurred are also reported to the DSMB, IRB, and NIDA for further review.

#### **20. Trial stopping rules**

The primary stopping rule would be based on a statistically significant ( $p < .05$ ) and clinically significant ( $d < -0.2$ ) finding in the wrong direction (i.e., experimental group doing worse than the control group) on the primary outcome, substance frequency scale. In consultation with the DSM monitor, the trial could also be stopped (or modified) if other unexpected issues come up suggesting that the intervention or research procedures are causing harm.

#### **21. Process of AE/SAE collection, assessing by PI and/or medical monitor and reporting**

Our study definitions of critical events to be monitored are:

- The expected Adverse Events (AE) measured directly as part of baseline and quarterly observations are the days of problems from AOD use, health problems interfering with responsibilities, mental health problems interfering with responsibilities, being disturbed by memories, behavioral problems, being homeless, family problems, illegal activity, arrests, in trouble with parole/probation.
- The expected Serious Adverse Events (SAE) measured directly as part of the quarterly observation are any medical ER/hospitalization, any mental health ER/hospitalization, and any incarceration. Deaths are documented both in follow-up logs and (if we have firsthand or reliable information) as in the negative event report discussed below.
- Unexpected AE/SAE (including deaths where we have details) will be documented the same day we find out about it with the negative event report. This includes documentation to code who was there, when/how it happened, where it happened, what actions were taken (e.g., referral to clinical supervisor, police report, hotline call).

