Participants assigned to the "RIMO" group will have a face-to-face meeting with the Linkage Manager (LM), who will engage the participants in a discussion about their willingness to go to MAT. Based on our prior trials and the pilot, we expect this meeting to take place in 1-4 working days following the OD. LM will use motivational interviewing (MI) techniques to: 1) discuss with participants the benefits of their decision to go to treatment, including activities they might enjoy as well as things they do not like about their alcohol/substance use, 2) provide personalized feedback to participants about the status of their condition based on responses to the assessment instruments, 3) help participants resolve ambivalence about their opioid use and move them toward a commitment to change by accessing treatment, 4) address existing barriers to treatment, e.g., assess Medicaid eligibility and assist with applications, problem-solve issues regarding childcare or transportation, 5) schedule a treatment appointment, 6) develop a reminder schedule for MAT appointments, and 7) problem

solve any transportation or other challenges that arise. The LM will contact participants 2-3 times/week for at least 4 weeks to ensure that participants complete detox and/or initiate and remain engaged in MAT. This includes working with the individual and the treatment provider to minimize missed doses, which can “reset” the dosing schedule. Specifically, the LM will follow-up with the treatment agency and/or participants to determine if they showed for their intake appointments and scheduled dosing for 30 days. For participants that miss a dose, the LM will contact them to discuss barriers and ways to remove them. Additionally, the LM and MAT provider will coordinate information on the participant’s barriers to treatment engagement (i.e., scheduling, transportation) and assist the participant in problem-solving solutions to support their treatment retention. During the first 30 days, the research team will provide bus cards for those in need.

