### **TRIAL EFFICACY**

#### **23. Plan for interim analysis (if applicable)**

Each annual DSM report will include an analysis of efficacy data. If any annual review reveals a significant difference in dependent variables (or AE or SAE) that goes AGAINST the experimental condition or

appears to be related to a study specific procedure, we will consult with the DSMB on the need to modify the protocol, study procedure, or even stop the study. As noted above, the stopping rule would be based on a statistically significant ( $p < .05$ ) and clinically significant ( $d < -0.2$ ) finding in the wrong direction.

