### **27. Content of DSM report**

Annual reports of data collected to date will include an enrollment update, the status of retention and disposition of participants (active, completed, and terminated), reviews of case flow, checks on randomization, implementation, method checks on measures, preliminary outcome analyses, expected and unexpected AE/SAE, all negative event forms, and any regulatory issues (amendments, protocol deviations, IRB reports, and QA issues).

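### The Section 23 harm trigger does not separate adverse events by how they were collected, so its unexpected-event part is open to surveillance bias against RIMO

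*Combined protocol and SAP*

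**What the plan says.** Section 21 sets up two collection routes. Expected AEs (ten kinds of problem) and expected SAEs (emergency visits or hospitalization, and incarceration) are measured at the quarterly interviews, which follow the same schedule in both arms. Section 8 keeps the interviewers blind to assignment. Unexpected events follow the second route: "Unexpected AE/SAE (including deaths where we have details) will be documented the same day we find out about it with the negative event report". Deaths go in the follow-up logs and, when the information is good enough, also on the negative event form.

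Section 27 brings both routes into one annual report, which is to contain "expected and unexpected AE/SAE, all negative event forms". Section 23 then sets the trigger: "If any annual review reveals a significant difference in dependent variables (or AE or SAE) that goes AGAINST the experimental condition", the team consults the board about changing or stopping the study. No section limits which events enter this comparison, and none asks for the source of a form-reported event.

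Contact with participants differs by arm. In Section 8, "The LM will contact participants 2-3 times/week for at least 4 weeks"; in Section 1 the same contact is weekly by telephone. These two statements contradict each other and must be reconciled. Linkage Managers also check with treatment agencies and re-contact people who refuse linkage. Controls get a brochure, plus the tracking and interviews that both arms receive.

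**The concern.** A between-arm comparison of event counts is fair only if an event of the same kind has the same chance of being recorded in each arm. The second route has no schedule and no arm-neutral source: an event is recorded if someone on the study hears of it. In RIMO there is an extra member of staff who may hear of it, directly or through a provider. With equal true risk, RIMO would tend to accumulate more forms.

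The monitor could then be consulted about a safety signal that reflects only how often participants were spoken to. With no source recorded, the monitor would have difficulty telling that apart from real harm.

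**Working it through.** The plan gives no capture rate and no incidence for unexpected events, so it has no figure to reproduce. The check has two parts.

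**1. Size of the contact difference.** Weekly contact for at least 4 weeks (Section 1) is at least 4 contacts. At 2-3 per week (Section 8) it is at least 4 × 2 = 8 to 4 × 3 = 12. One 4-week window covers 28/270 = 10% of a 9-month follow-up.

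**2. Illustrative false-signal probability.**

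Inputs:
- n = 175 per arm (Section 4).
- True risk p, equal in both arms: assumed 2%, 5% or 30%.
- Capture: assumed 0.90 in RIMO (dR), and 0.80, 0.70 or 0.60 in control (dC).
- Test: two-sided 0.05. Section 23 gives no separate threshold for the AE/SAE comparison, so this is also an assumption.

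Recorded events are A ~ Bin(n, p·dR) in RIMO and C ~ Bin(n, p·dC) in control. With p̄ = (A + C)/(2n),

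z = [(A − C)/n] / √[2p̄(1 − p̄)/n].

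The probability of a signal against RIMO is the sum of the exact binomial probabilities over all (A, C) with z > 1.96. For example, at p = 30% and dC = 0.60 the expected counts are 175 × 0.27 = 47.3 and 175 × 0.18 = 31.5, an apparent risk ratio of 1.50 with no true difference. At p = 5% they are 7.9 and 5.3.

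| Per arm | True risk | Control capture 0.80 | 0.70 | 0.60 |
|---|---|---|---|---|
| 175 | 2% | 0.031 | 0.043 | 0.059 |
| 175 | 5% | 0.041 | 0.067 | 0.107 |
| 175 | 30% | 0.094 | 0.259 | 0.524 |
| 88 | 2% | 0.018 | 0.022 | 0.026 |
| 88 | 5% | 0.030 | 0.044 | 0.063 |
| 88 | 30% | 0.068 | 0.155 | 0.302 |

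The lower rows approximate a first annual review: 350 participants over 24 months gives 175 in 12 months, or about 88 per arm. They ignore the fact that follow-up is then incomplete. With equal capture (0.90 in both arms) and 175 per arm, the probability is 0.023-0.026.

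**Advantage limited to the Linkage Manager window.** Suppose detection is complete in RIMO during a share w of follow-up and equals c (0.5-0.9) otherwise and in control, so that dR = w + (1 − w)c and dC = c. With one window, w = 28/270 = 0.104. At c = 0.5, dR = 0.104 + 0.896 × 0.5 = 0.552, a ratio of 1.10. Over c = 0.5-0.9 and true risks of 5-30%, with 175 per arm, the probability is 0.026-0.060. If the window were repeated after the 3- and 6-month sessions (an assumption), w = 84/270 = 0.311 and the range is 0.029-0.212.

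**The case against.** Much of the plan works against the concern. A reader might infer that the whole AE/SAE comparison is biased, but the expected events, including hospitalization and incarceration, come from identical interviews with blinded interviewers. A reader might also infer that deaths are recorded only on the form. Section 21 enters them in the follow-up logs as well, and Table 2.1 takes opioid-related deaths from CDC death records. Nor are controls without contact: the tracking steps in Section 1 apply to both arms. The RIMO sessions at 3, 6 and 9 months fall at the same time points as the interviews, and no section asks Linkage Managers to elicit adverse events.

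The consequence is also limited. The primary stopping rule in Section 20 rests "on the primary outcome, substance frequency scale", not on adverse events. The AE/SAE trigger leads to consultation, the PI classifies the relatedness of each unexpected event (Section 24), and the monitor sees every form. A safety screen that leans towards consultation can be defended. A real excess in controls would not be hidden from this trigger, which looks only for differences against RIMO.

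All of this stands, and it narrows the point without removing it. The tracking steps concern locating and scheduling, not asking about events. Follow-up logs depend on tracing, and the death records are specified for an outcome, not for the annual safety review. Relatedness review does not correct unequal counts, and Section 24 states no blinding for it. At 14-16 enrolments per month (Section 7), about 3 × 14 = 42 to 3 × 16 = 48 participants at any review during accrual would not yet have reached a 3-month interview. Apart from the death log, their post-randomization events can enter only by the form.

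**Conclusion.** The point holds for unexpected AEs and SAEs and for form-reported deaths. As written, Section 23 admits these to a between-arm test although the chance of recording them may differ by arm, and no section corrects for this. The documents support calling the comparison open to bias; they do not show that it is biased.

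The size runs from negligible to large and turns on incidence and capture rates that the plan does not give. The roughly 50% false-signal figure needs 30% incidence of unexpected events, 60% control capture throughout follow-up, and all 175 per arm. A reader should not take it as typical, since the commoner serious events are already in the interview stream. At 2-5% incidence the chance is 3-11% per look with 175 per arm, and about 2-6% with 88. The point merits a change because the remedy is cheap, not because a false signal is likely.

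**What to change.** - **Section 23:** base the formal between-arm AE/SAE test on sources collected the same way in both arms: quarterly interview items, deaths in the follow-up logs, and death records where available.
- **Section 27:** tabulate negative-event-form events by arm and by source of report (interviewer, tracker, Linkage Manager, provider). Have the monitor review all of them individually, so that events from Linkage Managers and providers can still prompt consultation on clinical grounds and the screen loses no sensitivity to harm.
- **Section 21:** complete a form for every known death in either arm, whether or not details are available.
- **Sections 1 and 8:** reconcile the two statements of Linkage Manager contact frequency, since they determine how large the contact difference is.

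The cost is some rewording of the monitoring plan, one source field on the existing form, and somewhat fewer events in the formal test.

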#### **22. AE/SAE follow-up plan**

The PI will work with the study's DSM monitor, Chestnut's IRB and NIDA to anticipate and minimize the risk of SAE and other study risk in advance. The PI will also monitor study implementation to verify assumptions and performance relative to these risks in general, including training staff to report unexpected SAE/AE and other study risks so that they can be reviewed and reported. Where there are more than expected SAE/AE, unexpected SAE or other study risks, the PI will work with the DSM monitor and Chestnut's IRB to modify procedures to address them and, if necessary, decide to suspend or stop the study.

### **TRIAL EFFICACY**

#### **23. Plan for interim analysis (if applicable)**

Each annual DSM report will include an analysis of efficacy data. If any annual review reveals a significant difference in dependent variables (or AE or SAE) that goes AGAINST the experimental condition or

appears to be related to a study specific procedure, we will consult with the DSMB on the need to modify the protocol, study procedure, or even stop the study. As noted above, the stopping rule would be based on a statistically significant ( $p < .05$ ) and clinically significant ( $d < -0.2$ ) finding in the wrong direction.

## **ADMINISTRATION OF DSM PLAN**

### **24. Responsibility of data and safety monitoring**

All unexpected AE/SAE and actions taken will be documented on the negative event form and reviewed within 48 hours by the PI, who will classify the incident as an AE, SAE, or other, the degree to which it is related to intervention or research procedures, and document any actions taken (with participant, reporting to IRB, reporting to DSMB). Any events that are attributed to the intervention or research procedure and any sentinel event will be reported within 48 hours to the DSMB, IRB, and NIDA for further review. We will use The Joint Commission (TJC) definition of a sentinel event as “any unanticipated event in a healthcare setting resulting in death or serious physical or psychological injury to a patient or patients, not related to the natural course of the patient’s illness.” A copy of the annual report, the findings and any correspondence will be forwarded to Chestnut’s IRB and our NIDA project officer as part of annual reporting.

### **25. Frequency of monitoring**

All interviews and intervention sessions will all be recorded. All will be reviewed until each staff person is certified. After that 2 recordings per person per month will be reviewed to sustain fidelity (more will be reviewed if problems are identify). Data will be downloaded cleaned and checked quarterly for quality assurance. The DSM Plan will be updated and reviewed by the IRB and DSM during the quarter prior to going into the field. The annual report will be given to the DSMB for external review approximately 2 to 4 weeks before our continuation is due to NIDA. Any directly observed or caused serious adverse event will be documented on the negative event form, reviewed and the PI and submitted to the DSMB, IRB, and NIDA within 48 hours.

